Hybrid Ablation Plus Medical Therapy for Persistent Atrial Fibrillation
(HYBRID-AF)

ClinicalTrials.gov ID: **NCT04190186**

March 03, 2025

Statistical Analysis Plan for the HYBRID-AF Trial

1. Introduction This Statistical Analysis Plan (SAP) outlines the planned statistical analyses for the HYBRID-AF Trial, which has concluded.

2. Study Objectives The HYBRID-AF Trial evaluates the effectiveness of Biotronik ICM-guided intervention in reducing atrial fibrillation (AF) burden in patients with symptomatic persistent AF post-ablation. The primary objective is to compare AF burden between months 3 and 15 post-ablation between the Biotronik ICM-guided arm and the conventional AF management arm.

3. Study Design

- Randomized, controlled trial with 90 subjects assigned 1:1 to either conventional AF management or Biotronik ICM-guided management.
- Follow-up assessments at 3, 6, 9, 12, and 15 months post-randomization.
- Primary and secondary endpoints will be analyzed according to the intent-to-treat (ITT) principle.

4. Endpoints

Primary Endpoint:

- AF burden, defined as the percentage of time a subject experiences AF between months 3 and 15 post-ablation, measured by the Biotronik ICM.

Secondary Endpoints:

1. Composite endpoint of:
 - Clinically significant (>30 min) atrial arrhythmia (AF, atrial flutter, or atrial tachycardia) detected by Biotronik ICM post-index ablation.
 - Symptomatic AF recurrence (any duration).
 - Repeat AF ablation.
 - Cardiac hospitalization.
 - Death.
 - Healthcare utilization (hospitalization, ED visits, unplanned office visits).
2. Incidence of atrial flutter or tachycardia post-ablation.
3. Incidence of repeat procedures.
4. Major adverse events requiring rehospitalization.
5. Quality of life (QOL) assessment.

5. Sample Size Justification Based on prior studies and preliminary data, AF burden is expected to be 25% in the conventional group and 16% in the intervention group, with a standard deviation of 15%. A Wilcoxon rank-sum test at a two-sided alpha level of 0.05 and 80% power determined that 90 subjects (with a 10% dropout rate) were required.

6. Statistical Methods

Primary Analysis:

- AF burden comparison between groups using the Wilcoxon rank-sum test.
- Descriptive statistics for median and interquartile range (IQR) of AF burden.
- Sensitivity analysis for missing data using multiple imputation.

Secondary Analyses:

- Kaplan-Meier survival analysis for time to first atrial arrhythmia event.

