- Cox proportional hazards regression for risk factors associated with AF recurrence.
- Poisson regression for healthcare utilization.
- Mixed-effects models for QOL changes over time.

Subgroup Analyses:

- Stratification by baseline AF burden, age, and sex.
- Sensitivity analysis excluding early dropout subjects.

7. Data Handling

- All analyses will follow an ITT approach.
- Missing data will be addressed using multiple imputation and sensitivity analyses.
- Data management will be conducted per Good Clinical Practice (GCP) guidelines.

8. Reporting and Interpretation

- All results will be reported with 95% confidence intervals and p-values.
- Statistical significance is defined as $p < 0.05$.
- Study findings will be presented in accordance with CONSORT guidelines.

9. Conclusion This SAP ensures rigorous and transparent statistical analyses for the HYBRID-AF Trial, aligning with ClinicalTrials.gov reporting requirements.

Hybrid Ablation Plus Medical Therapy for Persistent Atrial Fibrillation

Lead Principal Investigator: [name]

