17. DATA ANALYSIS PLAN

For the primary endpoint of AF burden, i.e. percentage of overall follow-up spent by the subject experiencing atrial arrhythmias, the Wilcoxon rank-sum test will be used to statistically compare the conventional group vs. the active treatment group.

For the secondary composite end point, we will perform longitudinal event-free survival analysis, defined by survival and freedom from atrial arrhythmias, re-ablation, and cardiac hospitalization. Event-free survival rates, as captured by the composite secondary endpoint, will be displayed using the method of Kaplan-Meier. We will use the log-rank test to non-parametrically compare the overall survival curves for the two treatments. The other secondary endpoints of atrial flutter/tachycardia recurrence, repeat ablation incidence, and major adverse events will be compared utilizing negative binomial regression tests to statistically compare the event rates in the two arms, using the natural log of follow-up time as an offset. Quality of life measures will be compared between the arms using the non-parametric Wilcoxon rank-sum test.

The estimate for the sample size necessary to compare AF burden at 12 months between the conventional AF management arm vs. the Bio-Monitor 3-guided repeat ablation arm will assume a 1:1 distribution of subjects between the two arms. Since most of the re-ablation procedures will be carried out based on ICM-detected subclinical AF recurrences, we conservatively expect a re-ablation rate of 50% in the intervention arm vs. 5% in the conventional arm (in which only clinical episodes will be treated and resumption of antiarrhythmic medical therapy is also allowed).

For the planned analysis of the primary end point of AF burden involving the Wilcoxon rank-sum test, a two-sided $\alpha = 0.05$ and power of 80% was assumed. Based on our preliminary data and our prior studies on AF burden (The HARMONY Trial, Circulation Arrhythmia and Electrophysiology, 2015), the 12 month primary outcome of AF burden is assumed to be 25% vs. 16% in the conventional group, with a standard deviation of 15% (a conservative estimate which allows for 10% drop-out). A reduction from 25% to 16% and 80% power,

with a drop-out rate of 10%, will result in a total sample of 90 patients.

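### SAP section 8 applies p < 0.05 to every result, so secondary, healthcare-utilization and subgroup findings can be called significant even if AF burden is not

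*Combined protocol and SAP*

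**What the plan says.** The rule is in SAP section 8. One line reads "All results will be reported with 95% confidence intervals and p-values". The next begins "Statistical significance is defined as" and sets the limit at p < 0.05, with no endpoint excepted.

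SAP section 4 names one primary endpoint, AF burden, and five numbered secondary endpoints: a composite, atrial flutter or tachycardia, repeat procedures, "Major adverse events requiring rehospitalization", and quality of life.

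Protocol section 17 gives each of the five a between-arm test:
- Composite: "We will use the log-rank test to non-parametrically compare the overall survival curves for the two treatments".
- Three event-rate endpoints: "The other secondary endpoints of atrial flutter/tachycardia recurrence, repeat ablation incidence, and major adverse events will be compared utilizing negative binomial regression tests".
- Quality of life: a Wilcoxon rank-sum test.

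SAP section 6 adds a Poisson model for healthcare utilization and subgroup analyses by baseline AF burden, age and sex. It does not itself assign a between-arm test to each secondary endpoint.

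Protocol section 17 attaches error rates to the primary only: "a two-sided $\alpha = 0.05$ and power of 80% was assumed". Neither document contains a multiplicity adjustment, a testing order, a condition that the primary succeed first, or a statement that secondary results are exploratory.

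**The concern.** Naming a single primary endpoint protects that endpoint's error rate. It does not settle what may be said about everything else. Under section 8 as written, a quality-of-life or healthcare-utilization p-value of 0.03 carries the same label as a primary p-value of 0.03, whatever AF burden shows.

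A missed primary is not a remote case. At the planned 80% power, AF burden misses 1 time in 5 (1 − 0.80 = 0.20) even if the assumed effect is real. The report could then present a secondary or subgroup result as a statistically significant effect of ICM guidance, and a reader could not tell from the plan that the result had no error control behind it.

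**Working it through.** The documents state no family-wise error rate, so there is no figure of theirs to reproduce. The check is what the stated rule implies.

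**Inputs**
- Threshold: two-sided 0.05 per test (SAP section 8; sidedness from SAP section 5 and protocol section 17).
- Number of secondary tests: 5, one per numbered endpoint (SAP section 4; protocol section 17: 1 log-rank + 3 negative binomial + 1 Wilcoxon).
- Expected re-ablation: 50% in the intervention arm vs 5% in the conventional arm (protocol section 17).
- Correlation among the test statistics: not given. It is assumed, with a range shown.

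**Step 1. All five nulls true, independent tests, either direction.**
1 − 0.95^5 = 0.226, or about 23%.

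**Step 2. Upper bound under any dependence.**
5 × 0.05 = 0.25.

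**Step 3. Benefit direction only.** Each two-sided test puts 0.025 in the favourable tail:
1 − 0.975^5 = 0.119, or about 12%. This is the figure that matches a false claim of benefit.

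**Step 4. Correlated tests, either direction.** The endpoints overlap. As listed in section 4 of both documents, the composite includes atrial flutter or tachycardia over 30 minutes, repeat ablation, cardiac hospitalization and healthcare utilization, which the protocol defines to include hospitalization for any cause. It therefore shares events with secondary endpoints 2, 3 and 4. Take five standard normal test statistics with common correlation ρ, c = 1.96 and X standard normal. The chance of at least one rejection is

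1 − E{[Φ((c − √ρ·X)/√(1−ρ)) − Φ((−c − √ρ·X)/√(1−ρ))]^5}.

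| Assumed ρ | At least one p < 0.05 |
|---|---|
| 0 | 22.6% |
| 0.2 | 21.8% |
| 0.3 | 20.9% |
| 0.4 | 19.7% |
| 0.5 | 18.3% |
| 0.8 | 12.7% |

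The figure falls below 20% at ρ of about 0.38.

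**Step 5. Four true nulls.** With re-ablation expected at 50% vs 5%, the null for repeat procedures is not expected to hold. For the other four, if independent:
- either direction: 1 − 0.95^4 = 0.185;
- benefit direction: 1 − 0.975^4 = 0.096.

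**Step 6. Adding the healthcare-utilization model as a sixth null test.**
1 − 0.95^6 = 0.265 if independent. Healthcare utilization is also a composite component, so independence is doubtful here too.

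**Step 7. Under the fix.** The only significance claim is AF burden at two-sided 0.05, so the chance of any false significance claim is at most 5%.

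**The case against.** The strongest reply is that this is a Phase 4 comparison of two strategies already in use. It has one primary endpoint, alpha and power attach to that endpoint alone, and a reader will know that the rest is supportive. Nothing in the text says a secondary endpoint may stand in for a failed primary. This is fair in part. The primary's 5% error is intact, and the possibility of substitution follows from the absence of any restriction, not from a stated intention. But section 8 is an explicit rule covering all results, and following it literally permits the label.

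Three stronger readings are tempting, and the documents do not support them:

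- **That the false-positive risk is simply above 20%.** This needs five true nulls and near-independent tests. The overlap between the composite and secondary endpoints 2 to 4, and the expected re-ablation difference, both count against those conditions. For false claims of benefit the independent figure is about 12%.
- **That subgroups push the risk above 40%.** Six within-stratum tests added to the five would give 1 − 0.95^11 = 0.431. But the SAP gives no cut-points, no number of levels and no statement that each stratum is tested. The three factors also re-divide the same patients, so the tests would not be independent. No subgroup figure can be derived from the plan.
- **That the remedy must be a fixed sequence in the listed order.** That would hold the family at 5%. It would also make repeat procedures, which the protocol expects to be more frequent in the intervention arm, a gate for what follows, and would put an adverse-event endpoint behind efficacy results.

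**Conclusion.** The gap is real: one threshold covers all results, and nothing separates confirmatory from nominal p-values. The plan therefore allows a significance claim for a secondary, healthcare-utilization or subgroup result after AF burden has failed.

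For the five secondary endpoints, the chance of at least one false p < 0.05 is about 23% in either direction if all nulls are true and the tests independent. The range is 22.6% down to 12.7% over assumed common correlations of 0 to 0.8. With four true nulls, independent, it is 18.5%. The correlations are assumptions. All of these figures are well above 5%, and the missing rule does not depend on which of them is nearest the truth.

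This does not undermine the primary analysis. It affects what else the trial may conclude, and it should be corrected.

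**What to change.** Replace the significance rule in SAP section 8 with:

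> Statistical significance at two-sided 0.05 is claimed for the primary endpoint (AF burden) only. Secondary, healthcare-utilization and subgroup results are reported with estimates, 95% confidence intervals and nominal p-values, and are not described as statistically significant.

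State also that the adverse-event endpoint sits outside any gate and is reported in full whatever the primary shows.

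Because SAP section 1 says the trial has concluded, date the change, disclose it in the report, and say whether it was made before or after outcome data were seen.

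The cost is one paragraph plus the disclosure. No data, subjects or analyses change, and every estimate and interval is still reported. The real price is that fewer results may be called significant, including any secondary effect that is genuine.

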1. PURPOSE OF STUDY

To prospectively investigate the efficacy of an insertable cardiac monitor-guided atrial fibrillation (AF) management in reducing subsequent atrial arrhythmia burden in patients with persistent AF undergoing ablation. This is a Phase 4 study, and we are comparing two management strategies that are currently employed in clinical practice.

2. BACKGROUND AND RATIONALE

Percutaneous catheter ablation to achieve pulmonary vein electrical isolation is an effective and recommended treatment for paroxysmal atrial fibrillation. Catheter ablation for persistent AF is more complex, often may involve ablation of additional targets that maintain AF. Nevertheless, recurrence rate after a single ablation procedure in patients with persistent AF is in the range of 50%-70% at 1-year, and 70%-90% at 2-years. Accordingly, catheter ablation for persistent AF has been associated with less favorable outcomes. Continued antiarrhythmic drug (AAD) use, or redo AF ablation procedures often can improve outcomes in persistent AF patient's further substrate deterioration if sub-clinical AF recurrences are detected by an insertable cardiac monitor. Thereby, we propose utilizing the Biotronik ICM (BioMonitor3® or future generation of Biotronik ICM) in persistent AF patients following AF ablation to guide post ablation strategies of AAD treatment and/or repeat AF ablation and to continuously post-AF ablation to reduce the burden of atrial arrhythmia. However, these management strategies are currently limited to a subset of patients who present with symptomatic AF post-AF ablation, possibly late in the clinical course, due to lack of appropriate continuous monitoring tools following the procedure. With the Biotronik insertable cardiac monitor (ICM) in persistent AF patient's post-AF ablation, one may be able to provide patient-specific tailored management, and to identify those who may benefit from early intervention to prevent monitor AF burden. We hypothesize that early patient-specific intervention, guided by the Biotronik ICM, will be associated with a significant reduction in AF-burden at 15 months following ablation for persistent AF.

Of note contemporary referral for ablation among patients with persistent AF does not require failure of at least one AAD. Recent clinical trials have demonstrated the utility of ablation as first line therapy for patients with atrial fibrillation. Therefore, many patients with persistent AF are referred for AF ablation today without being on an AAD (Calkins, et al. Heart Rhythm, Vol 14, No 10, October 2017), thereby leading to higher recurrence rates in this population.

Patients with persistent atrial fibrillation remain a challenging population in terms of achieving and maintaining sinus rhythm. Recent studies (Heart Rhythm. 2018 Mar; 15(3):363-368) have reported pulmonary vein isolation ablation to be a "safe, effective, and efficient" treatment. However, even with extensive ablation of PV isolation plus other targets, the recurrence of atrial arrhythmia post ablation for persistent AF ranged from at

least 41 to 54% with periodic ambulatory ECG monitors (Schreiber, et al. *Circ Arrhythm Electrophysiol* 2015; 8:308–317.; Verma, et al. *N Engl J Med* 2015; 372:1812–1822.). Most clinicians suspect the recurrence rates to be substantially higher if more robust surveillance is obtained. We had previously reported on the efficacy of hybrid therapy combining ablation of atrial flutter circuit and medical therapy for patients with atrial fibrillation who converted to atrial flutter with medical antiarrhythmics (Huang, et al., *JCE* May 1998, 9(5):462-469), and noted the importance of maintaining medical antiarrhythmic therapy to achieve long term substrate modification leading to sinus rhythm. A recent study reported >90% patients who experience AF events during the typical 3 months blanking period actually develop recurrent atrial arrhythmia by 1 year (Willems et al. *Circ Arrhythm Electrophysiol* 2016;9(8)). Early recurrence of AF during the post ablation blanking period may be more aggressively treated to help reduce risk of late recurrence of AF. Therefore, in our study, we propose to initiate monitoring AF events during the blanking period, starting from the first month post-AF ablation (to allow sufficient time for post ablation healing). On the other hand, it is postulated that a subgroup of patients with persistent AF may respond well to repeat ablation alone, similar to patients with paroxysmal AF (Kirchhof, Calkins. *European Heart Journal*, 2017 Jan; 38(1):20–2). Thus, a management strategy of uniform continued AAD post ablation for persistent AF will result in unnecessary medical therapy in responders to the procedure. We therefore hypothesize that a patient-specific management strategy that incorporates continuous monitoring with Biotronik ICM will result in improved outcomes and resource utilization compared to conventional management in this high-risk population.

3. ADMINISTRATIVE ORGANIZATION

The University of Rochester is the Coordination and Data Center (CDC) for the multisite study. The University of Rochester Medical Center, Rochester Regional Health, Michigan Heart and the Cardiology Research Associates will be the participating centers in this trial. Each site will obtain separate local IRB approvals. The University of Rochester CDC will provide each site with the study protocol and a model consent form, along other relevant subject study materials. As the Coordination and Data Center (CDC), the University of Rochester will provide comprehensive training on the study protocol, study operations, and the electronic data capture system (TrialMaster). All training will be documented for each enrolling site.

The University of Rochester is the Study Sponsor and is receiving funding from BIOTRONIK for conducting this research study.

4. STUDY DESIGN

This is a multi-site, randomized clinical trial of approximately 90 subjects with 45 subjects in each arm randomized (1:1) to conventional AF management vs. Biotronik ICM-guided AF management following ablation for persistent AF. The study subject population will include subjects with history of persistent atrial fibrillation (sustained AF episode lasting more than 7 days, but less than 1 year), according to current guideline indications for persistent AF ablation and ICM (Biotronik ICM) implantation. Clinical and functional data will be

captured related to: activity, heart rate, blood pressure, weight, quality of life status, and clinical events.

A total of 4 high-volume sites will be enrolling subjects for this study. Estimated enrollment will be 1-2 subjects per study site per month. Patients will be enrolled at the time of the AF ablation and will be followed for 15 months after a 3 month blanking period following AF ablation. The planned study startup period is 3 months with an enrollment period of 10 months, a follow-up period of 15 months, and 2 months for closeout and analysis for a total of 30 months (2.5 years).

The CDC is responsible for data management, analysis, and coordination of logistics. The enrolling sites will manage all subject recruitment activity and data collection per protocol as well as interact with the CDC and enrolling site study team regarding study operations. The CDC will be responsible for overall study management, data management, data reporting, and center communications for the study.

Primary Endpoint

The primary endpoint is atrial fibrillation (AF) burden between months 3 and 15 after the ablation procedure (to exclude the first 3 month blanking period) by the Biotronik ICM in the conventional AF management versus the of Biotronik ICM-guided AF management arm.

Secondary Endpoints

1. Composite end point of:

- clinically significant (>30 min) atrial arrhythmia (atrial fibrillation, atrial flutter or atrial tachycardia) as detected and documented by Biotronik ICM after the performance of the index AF ablation procedure (excluding the initial 3-month blanking period), or
- symptomatic AF recurrence (regardless of duration), or
- repeat AF ablation, or
- cardiac hospitalization, or
- death
- healthcare utilization, defined as hospitalization for any cause, ED visits, and unplanned office visits

For the primary outcome, no episode of AF occurring within the initial 3-month blanking period after ablation will be counted, although these will be tracked.

[figure not shown]
2. Incidence of atrial flutter or tachycardia after the index ablation procedure

3. Incidence of repeat procedures

4. Major adverse events requiring rehospitalization during follow-up

5. Quality of life (QOL) as assessed by Atrial Fibrillation Effect on QualiTy-of-life (AFEQT) questionnaire

Figure 1: Study Design

* Based on Biotronik ICM data after 1st Month

** Escalate to medical therapy or repeat AF Ablation based on current treatment (i.e. no treatment will be escalated to the AAD or repeat ablation, and if on AAD will be escalated to AF ablation).

*** Biotronik ICM data on subclinical AF will not be provided to the treating physician

As detailed in Figure 1 subjects who agree to participate in the study by signing the IRB-approved informed consent are randomized 1:1 into:

The Intervention ICM-based AF management Arm

- In the intervention arm, the ICM obtained data will be actively used to guide and monitor treatment (See Figure 2A and B). A report of AF data (comprising the total number of episodes, duration, average heart rate response, and correlation with patient-reported symptoms) will be provided to the treating physician/nurse at monthly intervals, starting from the first month post-AF ablation from the study team comprised of electrophysiologists and cardiologists. A general recommendation for early intervention with AAD continuation/resumption or redo AF ablation will be provided to the treating physician if recurrent AF episodes are detected by the ICM (≥ 2 episodes at a duration of ≥ 6 minutes each), even without the presence of clinical symptoms. However, the final decision regarding management will be left to the discretion of the treating physician.
 - Management during the blanking period: Treatment with AAD after ablation will be left to the discretion of the treating physician per standard of care. If the patient is on an AAD after ablation, medical therapy with AADs in the intervention arm will continue for 3 months after the index CA procedure arm. Symptomatic AF recurrences during the blanking period will be treated with cardioversion. If, either SCAF (as defined above and in Figure 2A) is detected by the ICM or symptomatic AF recurrence occurs after one-month post-ablation (i.e. during the second or third months), AAD therapy will not be discontinued at 3 months per protocol (or will be initiated for those not treated with an AAD after ablation). AF recurrence during the blanking period will not be an indication for re-ablation.
 - Management after the blanking period: If SCAF recurrences detected by the ICM (as defined above and in Figure 2B) or if clinical recurrence occurs after the blanking period, treatment will be escalated as follows:
 - If the patient is not on an AAD after the blanking period, treatment with an AAD will be resumed (to the same drug discontinued at 3 months) or initiated (type of AAD will be left to the decision of the treating physician as per standard of care). Alternatively, if the patient does not tolerate or does not wish treatment with an AAD, the patient can be referred for repeat AF ablation.
 - If AF recurrence occurs on AAD, the patient will be referred for re-ablation.
 - The ICM-derived heart rate monitoring data will also be used for improved rate control (with a target mean heart rate of $<80-100$ bpm) regardless of atrial rhythm.

- An ad hoc adjudication committee will be formed to review and review all ICM interrogations. The committee will consist of Drs. [name], [name], [name], and [name]. The final adjudication of each arrhythmic event will be captured in the study database for the analysis of study endpoints and will not be used to guide management.
- The ICM report of AF data (comprising the total number of episodes, duration, average heart rate response, and correlation with subject-reported symptoms) will be provided to the treating physician/nurse at monthly intervals, starting from the first month post-AF ablation.
- In-clinic follow up visits as scheduled for subjects per standard of care and will occur at 3, 9, and 15 months. These visits will include a medical assessment and subjects will be questioned about clinical and unexpected medical (adverse) events.
- Phone follow-up visits will be conducted by the study team at 6 and 12 months as part of the study. The study team will perform a medical assessment, and ask questions about medication changes, along with clinical and unexpected medical (adverse) events as part of these follow-up phone calls.
- Chart reviews will be performed by the study team at each time point and include data about clinical history, medications, ablation procedure, device implantation, and follow-up data will be collected from the medical record.
- Quality of life questionnaire will be completed on paper by the patient at baseline and 15 months as part of the research study activities.
- ECGs performed as standard of care at Baseline, 3 month, 9 month, and 15 month.
- Endpoint assessment defined as AF burden, quality of life, and healthcare utilization (comprising the total of unplanned clinic visits, hospitalizations, repeat ablations, or death at 15 months.

Figure 2A: Management protocol for AF recurrence at Months 2 or 3 Post Ablation in the Intervention Arm*

[figure not shown]
[figure not shown]

Figure 2B: Management Protocol for AF Recurrence after 3 Post Ablation in the Intervention Arm

***If the patient is not on an AAD after the ablation, AAD will be initiated during the blanking period and continued post-blanking if there is ≥ 2 SCAF, 1 SCAF > 6 h or clinical recurrence. The type of AAD will left to the discretion of the treating physician as per standard of care. Repeat ablation can be offered if the patient does not tolerate or wish treatment with an AAD.**

Conventional AF Management Control Arm

- In the control arm, ICM data on SCAF recurrence will not be used to guide management. Management of clinical AF recurrence in the conventional management arm will be left to the discretion of the treating physician. The treating physician has access to all ICM data as standard of care and can use it per their discretion.
 - Management during the blanking period (ER): AAD management in the conventional arm, will be left to the discretion of the treating physician since

current guidelines do not provide specific recommendations (ref).

Symptomatic AF recurrences during the blanking period will be treated with cardioversion and SCAF detected by the ICM will not drive management.

- Management after the blanking period (LR): If the patient was on medical therapy with an AAD, it will be discontinued after 3 months in the conventional arm, unless considered necessary by the treating physician. SCAF detected by the ICM will not drive management.
- Patients will attend scheduled in-clinic follow up visits at month 3, 9, and 15 as part of standard of care. These visits will include a medical assessment and questions about clinical and adverse events.
- Chart reviews will be performed by the study team at each time point and include data about clinical history, medications, ablation procedure device implantation, and follow-up data will be collected from medical record.
- Quality of life questionnaire complete on paper by the patient at baseline and 15 months as part of the research study activities.
- Phone follow-up visits will be conducted by the study team at 6 and 12 months. The study team will perform a medical assessment, and ask questions about medication changes, along with clinical and unexpected medical (adverse) events as part of these follow-up phone calls.
- ECGs performed as standard of care at Baseline, 3 months, 9 months, and 15 month.
- Endpoint assessment defined as AF burden, quality of life, unplanned clinic visits or hospitalizations, repeat ablation, death at 15 months.

